9.4.5. ICH Listings

ICH: Listings					
No.	Population	IDSL / Example Shell	Title	Programming Notes	Deliverable
Subject Disposition					
1.	As-Treated	Listing 1	Subject Disposition for Years 2-5 Post-treatment Follow-up Period		IA SAC, SAC

ICH: Listings					
No.	Population	IDSL / Example Shell	Title	Programming Notes	Deliverable
Baseline/Demographic Characteristics					
2.	As-Treated Any Year 2 to 5 Follow-Up	Listing 2	Demographic and Baseline Characteristics		IA SAC, SAC
3.	As-Treated Any Year 2 to 5 Follow-Up	Listing 3	Listing of Race		IA SAC, SAC
Concomitant Medication (First exposure to commercial Benlysta, other than study treatment in Year 1)					
4.	As-Treated	Listing 4	Listing of Subjects Receiving First Commercial Benlysta including Week 52 and Years 2-5 Post-treatment Follow-up		IA SAC, SAC
Safety					
5.	As-Treated	Listing 5	Listing of Survival Status for Years 2-5 Post-treatment Follow-up		IA SAC, SAC
6.	As-Treated	Listing 6	Listing of Deaths for Years 2-5 Post-treatment Follow-up		IA SAC, SAC
7.	As-Treated	Listing 7	Listing of Subjects with New Malignancies for Years 2-5 Post-treatment Follow-up		IA SAC, SAC
Protocol Deviations					
8.	As-Treated Any Year 2 to 5 Follow-Up	Listing 8	Listing of Important Protocol Deviations for Years 2-5 Post-treatment Follow-up Period	ICH E3	IA SAC, SAC

9.5. Appendix 5: Example Mock Shells for Data Displays

See separate Mock Shell TFL document.

Division: World Wide Development

Retention Category: GRS019

Information Type: Reporting and Analysis Plan

Title:	Reporting and Analysis Plan (RAP) for BEL115467, A Randomized, Double-Blind, Placebo-Controlled 52-Week Study to Assess Adverse Events of Special Interest in Adults with Active, Autoantibody-Positive Systemic Lupus Erythematosus Receiving Belimumab
---------------	--

Compound Number: GSK1550188

Effective Date: 18-OCT-2018

Description: This is a global, multi-center, randomized, double-blind, placebo-controlled, 52-week study to assess mortality and adverse events of special interest in adults with active, autoantibody-positive systemic lupus erythematosus (SLE) receiving belimumab. Subjects will receive belimumab or placebo through Week 48 with a final visit conducted at Week 52 and standard therapy will be received throughout the study. Subjects will be assessed for malignancies including non-melanoma skin cancers (NMSC), serious infections, opportunistic infections and other infections of interest, selected serious psychiatric events, suicidality, and serious infusion and hypersensitivity reactions. All-cause mortality will be reported. All other serious adverse events regardless of causality will also be recorded. Efficacy endpoints are secondary in nature. Following the 52-week study, all subjects will be contacted annually through Year 5 to assess mortality and malignancy (including NMSC). This Reporting and Analysis Plan (RAP) prospectively describes the safety and efficacy analyses that will be performed through the Week 52 treatment period. Details of the planned summaries for the post-treatment follow-up for Years 2 to 5 will be described in a separate RAP.

Subject: Systemic Lupus Erythematosus, SLE, belimumab, GSK1550188, Benlysta, efficacy, safety, placebo, mortality, adverse events of special interest.

Author's Name, Title and Functional Area:

PPD
Statistics Leader
Clinical Statistics

Date: 18-OCT-2018

Approved by:

PPD
Senior Statistics Director
Clinical Statistics

Date: 17-OCT-2018

PPD
Programming Manager
Clinical Programming

Date: 18-OCT-2018

PPD
Director, Clinical Programming
Clinical Programming

Date: 17-OCT-2018

PPD
Clinical Development Director
Clinical Development

Date: 17-OCT-2018

PPD MD
Clinical Development Director
Clinical Development

Date: 18-OCT-2018

PPD

Global Clinical Development Manager

 - 16.4. Disclosure Outputs 82

ABBREVIATIONS

ACR	American College of Rheumatology
ADaM	Analysis Data Model
AE	Adverse Event
AESI	AEs of special interest
Anti-dsDNA	Anti-double-stranded DNA
ATC	Anatomical Therapeutic Chemical
AUC	Area under the curve
CDISC	Clinical Data Interchange Standards Consortium
CI	Confidence Interval
CIL	Clinical investigative lead
CMQ	Customized MedDRA Query
CRF	Case Report Form
C-SSRS	Columbia Suicide Severity Rating Scale
DBF	Database freeze
DBR	Database release
eCRF	Electronic Case Report Form
EMA	European Medicines Agency
GCP	Good Clinical Practice
IDMC	Independent Data Monitoring Committee
IDSL	Integrated Data Standards Library
IM	Intramuscular(ly)
IP	Investigational Product
ITT	Intention-to-treat
IV	Intravenous(ly)
IXRS	Interactive response system
MedDRA	Medical Dictionary for Regulatory Activities
MM	Medical monitor
NMSC	Non-melanoma skin cancer
NTM	Non-tuberculous mycobacterium
PSAP	Program Safety Analysis Plan
PSRQ	Possible Suicidality Related Questionnaire
PT	Preferred Term
RAP	Reporting and Analysis Plan
SAC	Statistical Analysis Complete
SAE	Serious Adverse Event
SC	Subcutaneous(ly)
SD	Standard deviation
SDAC	Statistical Data Analysis Center
SDTM	Study Data Tabulation Models
SELENA	Safety of Estrogen in Lupus National Assessment
SLE	Systemic Lupus Erythematosus
SLEDAI	Systemic Lupus Erythematosus Disease Activity Index
SLICC	Systemic Lupus International Collaborating Clinics
SOC	System Organ Class
SRT	Safety Review Team
TB	Tuberculosis

TLFs
WOCF

Tables, Listings and Figures
Worst Observation Carried Forward

Trademark Information

Trademarks of the GlaxoSmithKline group of companies
BENLYSTA

Trademarks not owned by the GlaxoSmithKline group of companies
SAS

1. INTRODUCTION

This reporting and analysis plan (RAP) documents the planned summaries through the Week 52 treatment period for the HGS1006-C1113 study. The study will be reported under its GSK study number BEL115467. A separate RAP will be produced to document the planned summaries of the post-treatment follow-up for Years 2 to 5.

This is a global, multi-center, randomized, double-blind, placebo-controlled, 52-week study to assess mortality and adverse events of special interest (AESI) in adults with active, autoantibody-positive systemic lupus erythematosus (SLE) treated with belimumab plus standard therapy vs placebo plus standard therapy. Following the 52-week study, all subjects will be contacted annually through Year 5 (Week 260) to assess mortality and malignancy (including non-melanoma skin cancers [NMSC]).

This RAP is based upon the following study documents:

- Study Protocol Amendment 03 (May 22, 2017)
- Final Case Report Form (CRF) Version 6.4 (February 05, 2018)
- Program Safety Analysis Plan (PSAP) Version 6 (October 2, 2018).
Note: for reporting purposes, the most current version of the PSAP at the time of database freeze (DBF) will be used. For reference, sections of the PSAP that are relevant to reporting are given in [Appendix 6: PSAP Sections for AESI Reporting](#). The most current MedDRA version at the time of database freeze (DBF) will be used.

2. STUDY OBJECTIVES AND ENDPOINTS

2.1. Study Objectives

To evaluate the following in adult SLE subjects receiving belimumab plus standard therapy versus subjects receiving placebo plus standard therapy:

- Mortality and adverse events of special interest (AESI) over 1 year (through 52 weeks).
- Corticosteroid reduction during Weeks 40-52.

2.2. Study Endpoints

2.2.1. Safety Endpoints

- All-cause mortality
- Serious infections (including serious opportunistic infections and any event of TB or TB reactivation)
 - See clarification in Section [2.2.3](#) (this endpoint will be referred to in the RAP as Serious Infections)

- Non-serious opportunistic infections and other infections of interest (protocol Appendix 2)
 - See clarification in Section 2.2.3 (this endpoint will be referred to in the RAP as Opportunistic Infections and Other Infections of Interest)
- Non-melanoma skin cancers (NMSC)
- Malignancies (excluding NMSC)
- Psychiatric events suggesting serious mood disorders and anxiety
- Suicidality (using C-SSRS; see protocol Appendix 4 and Appendix 5)
- Serious infusion and hypersensitivity reactions
- All serious adverse events (SAEs)

Section 9.5.12 provides definitions for all the protocol-defined AESIs. Section 2.2.3 provides the rationale for cases in which these may differ from the protocol.

2.2.2. Efficacy Endpoints

The major efficacy endpoint is:

- Percent of subjects whose average prednisone (or equivalent) dose has been reduced by $\geq 25\%$ from baseline to ≤ 7.5 mg/day during Weeks 40 through 52 in subjects receiving greater than 7.5 mg/day at baseline.

Other efficacy endpoints include:

- Use of immunomodulatory medications to treat SLE.
- Number of hospitalizations per patient.
- Percent of patients hospitalized.

Systemic Lupus International Collaborating Clinics (SLICC)/American College of Rheumatology (ACR) Damage Index will be recorded at baseline and at Week 52 to permit assessment of accrual of damage in subjects who may be followed in a subsequent study.

Section 2.2.3 provides the rationale for cases in which these may differ from the protocol.

2.2.3. Changes to the Protocol Defined Statistical Analysis Plan

Changes/clarifications from the original planned summaries specified in the protocol are as follows:

- Whilst the protocol description of the AESI for serious infections was stated to include “any event of TB or TB reactivation”, this has been defined in the RAP as All Serious Infections from the MedDRA ‘Infections and Infestations’ System Organ Class (SOC) aligned with the focus on serious infections. Hence any non-serious events, including those of ‘TB or TB reactivation’, would not be included in the endpoint but will be summarized separately.

- Whilst the protocol description of the AESI “Non-serious opportunistic infections and other infections of interest” refers to only non-serious events, the main summary will be of overall incidence (i.e., serious and non-serious events) aligned with focusing on all events of opportunistic infections and other infections of interest. Supplemental summaries of study agent related non-serious events will be produced, which will include non-serious opportunistic infections and other infections of interest. The endpoint will be derived using the “All infections” definition from the PSAP, Section 16.3 (See [Appendix 6: PSAP Sections for AESI Reporting](#)). This definition encompasses all infections of interest as defined in protocol Appendix 2. See Section [9.5.12](#).
- For the mortality endpoint, the protocol specifies that a hazard ratio (and 95% confidence interval [CI]) for belimumab vs placebo will be estimated using a Cox Proportional Hazards model. However due to the small number of events and low incidence rate, estimation using a difference in rates (and 95% CI) is considered more informative and so this supplemental analysis will not be conducted. A Kaplan-Meier curve and cumulative mortality counts by visit will be generated to illustrate the time profile.
- For the major efficacy endpoint (steroid dose reduction), the protocol states that if a subject switches immunomodulatory medications for reasons other than toxicity or lack of availability they should be considered a non-responder. However, the eCRF has not been designed to collect data on reasons for switches and therefore all new immunomodulatory agents to treat SLE will render a subject a non-responder in the analysis. Hence, subjects who switch will be considered non-responders regardless of the reason for switching. Additionally prednisone analyses and summaries are based only on steroids used to treat SLE (see Section [9.5.16](#) and Section [12.1.1](#)).
- “Immunomodulatory medications” will be identified as immunosuppressants (ATC code beginning “L04A”) plus cyclophosphamide and mercaptopurine, per the definition used across the Benlysta program.
- The number of hospitalizations per patient and percent of patients hospitalized will be derived from the SAE data. See Section [9.3](#) for further detail.
- SLICC/ACR Damage Index is not explicitly stated as an endpoint in the protocol. However, this is an endpoint of interest and therefore analyses will be performed as described in Section [12.2.3](#).

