8.5 Endpoints and Analysis

8.5.1 Safety Endpoint Definitions and Measurements

The table below describes the safety endpoints and measures collected in the study. All events shown in the table will be collected.

All-cause mortality
Serious Infections (including serious opportunistic infections and any event of TB or TB reactivation)
Non-serious opportunistic infections and other infections of interest (Appendix 2)
Malignancies (excluding NMSC)
Non-melanoma skin cancers
Psychiatric events suggesting serious mood disorders and anxiety
Suicidality (using C-SSRS; Appendix 4 and Appendix 5)
Serious Infusion and Hypersensitivity Reactions
All SAEs

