8.5.2 Analysis of Safety Endpoints

Mortality and AESI will be analyzed using an estimation paradigm. The difference in the rates of all prespecified AESI and all cause mortality, between the belimumab and the placebo groups will be evaluated with a 2-sided 95% CI. Deaths will also be described in detail, including, in the belimumab group, assessment of relationship to belimumab treatment.

For all cause mortality, the hazard ratio (and its 95% CI) for belimumab vs placebo will be estimated using the Cox proportional hazard model, without adjustment for baseline randomization factors. The time to death will be censored at the last follow-up by the end of the study for subjects who are alive.

SAEs will be analyzed descriptively only. The frequency and rate of serious adverse events will be tabulated by MedDRA system organ class (SOC) and preferred term. The SAE rates may also be reported adjusted for subject years.

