9.5.12. Mortality and Protocol-Defined AESI

Mortality status will be derived from the SAE data, where outcome is fatal.

The derivation for the protocol-defined AESIs are provided in the table below. Treatment emergent AESIs (see Section 9.5.13 and Section 9.5.15) only will be summarized.

Where the protocol defined AESI utilize definitions from the PSAP, the detailed derivations from the PSAP are provided in [Appendix 6: PSAP Sections for AESI Reporting](#). AESI are identified per the preferred terms and other criteria described in the PSAP.

Protocol-Defined AESI (see Section 2.2.1 and Section 2.2.3 for clarification)	Definition	Programming Derivation (Protocol Definition)
Serious infections	SAEs within Infections and Infestations SOC.	SOC=Infections and Infestations & AESER = 'Y'
Opportunistic infections and other infections of interest	"All Infections" per PSAP definition to cover all OI and infections of interest.	CQ06NAM ne " or CQ07NAM ne " or CQ08NAM ne "
Non-melanoma skin cancers (NMSC)	NMSC per PSAP definition.	CQ00MLFL = 'Y' and CQ03NAM ne " and CQ03NMFL = 'Y'
Malignancies (excluding NMSC)	PSAP defined, "all malignancies excluding NMSC".	[CQ00MLFL = 'Y' and (CQ01NAM ne " or CQ02NAM ne " or (CQ03NAM ne " and CQ03NMFL ne 'Y'))] Or (CQ04NAM ne " and CQ04NPFL = 'Y')
Psychiatric events suggesting serious mood disorders and anxiety	Serious events from the depression CMQ (PSAP defined – depression including mood disorders and anxiety).	CQ09NAM ne " and AESER = "Y"
Suicidality (C-SSRS)	Any treatment-emergent C-SSRS suicidal ideation (1-5) or suicidal behavior (6-10) (defined in Section 9.5.15) – i.e. maximum ideation score worsens relative to pre-treatment or maximum behavior score worsens relative to pre-treatment	C-SSRS Ideation categories 1-5 and Behavior categories 6-10; any subject with ideation or behavior that is treatment-emergent (defined in Section 9.5.15).
Serious infusion and hypersensitivity reactions	Serious infusion and hypersensitivity reactions per the PSAP definition. Includes all SAEs from the anaphylactic reactions CMQ broad search (see Section 11.2.4, includes events on the day of the infusion or within 3 days after the infusion).	CQ05NAM ne " and AESER='Y' and AEINF3FL='Y'

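### The Week 52 RAP redefines both infection AESIs, so in the supplied text neither endpoint as the protocol words it has a planned difference and 95% CI

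*SAP*

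**What the plan says.** Protocol 8.5.1 lists two infection endpoints: "Serious Infections (including serious opportunistic infections and any event of TB or TB reactivation" and, separately, "Non-serious opportunistic infections and other infections of interest (Appendix 2". Protocol 8.5.2 says that the difference for every prespecified AESI "between the belimumab and the placebo groups will be evaluated with a 2-sided 95% CI". Protocol 8.1 and RAP 2.3 both call this the main purpose of the study.

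RAP 2.2.3 (the Week 52 plan in the SAP document) changes both endpoints and gives its reasons.

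- **Serious infections.** The endpoint is limited to serious events: "Hence any non-serious events, including those of ‘TB or TB reactivation’, would not be included in the endpoint but will be summarized separately". Section 9.5.12 codes it as "SOC=Infections and Infestations & AESER = 'Y", with no TB clause.
- **Infections of interest.** The RAP acknowledges that the protocol means non-serious events only, but says "the main summary will be of overall incidence (i.e., serious and non-serious events". Section 9.5.12 codes it with the PSAP all-infections flags and no seriousness condition. For the non-serious part, "Supplemental summaries of study agent related non-serious events will be produced, which will include non-serious opportunistic infections and other infections of interest".

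Section 11.1.2 gives the difference and 95% CI for the AESIs as coded in 9.5.12. The rows keep the protocol-defined label in Tables 2.05 and 2.06.

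**The concern.** A reader of Tables 2.05 and 2.06 will take rows labelled protocol-defined to be the protocol's endpoints. Two of them are not. The protocol grouped TB with serious infections whatever its seriousness, and it kept the non-serious infections of interest apart. Under the RAP, a TB imbalance in non-serious events cannot show in the serious-infections row, and an imbalance in serious opportunistic infections or zoster moves both rows. Infection is one of the named safety objectives (protocol 1.3), and the study is estimation-only. The definitions of the rows that carry intervals therefore largely determine what the study reports.

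**Working it through.** **The plan's own precision figure.** The only one is ±0.46% for mortality (protocol 8.4 and 8.4.1, RAP 5.1); none is given for infections. With half-width = 1.96 × √(2p(1−p)/n):

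- p = 0.68%, n = 2,500 per arm: 0.456 points
- p = 0.564%, n = 2,000 per arm: 0.464 points

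Both round to 0.46. The figure is reproduced and is not in dispute. It confirms the simple asymptotic method and 2,000 per arm as the basis for what follows.

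**The definitions side by side.**

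| Event | Protocol 8.5.1 | RAP 9.5.12 |
|---|---|---|
| Serious infection not of special interest | serious | serious |
| Serious opportunistic infection | serious | both rows |
| Serious zoster or TB | serious (also of interest, if non-serious qualifies only the opportunistic infections) | both rows |
| Non-serious TB | serious, and also listed in Appendix 2 as of interest | of interest only |
| Other non-serious infection of interest | of interest | of interest |

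The RAP column assumes that the infection queries' terms sit in the Infections and Infestations SOC.

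**Whether other planned output recovers the protocol endpoints.**

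- RAP Table 1 has non-serious AESIs if study-agent related, or if common (at least 1%). Both are on-treatment only, with no difference or interval stated. A filter on investigator causality is not the protocol endpoint.
- RAP Table 1 also has all AESIs and SAEs by SOC and PT for both periods, as counts and percentages.
- RAP 11.2.4 gives all and serious rows for infections of special interest, and a non-serious row for active TB, with subjects, percentages and number of events. Non-serious *event* counts follow by subtraction. Non-serious *subject* counts do not, because one subject can have both kinds. Appendix 2 also covers latent TB, which an active-TB row leaves out.

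**Size of the overlap.** Serious infections of special interest, protocol Table 1-2:

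- Placebo: 5 + 3 + 7 = 15 of 675 + 280 + 235 = 1,190, or 1.26%
- Belimumab: 19 + 8 + 11 = 38 of 1,458 + 556 + 470 = 2,484, or 1.53%

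At 2,000 per arm this is 0.0126 × 2,000 ≈ 25 and 0.0153 × 2,000 ≈ 31 subjects. Protocol Table 1-3 puts serious infections at 5% in either group, or 100 per arm. Roughly 25% to 31% of subjects in the serious-infections row would therefore also be in the other row. The share is approximate, because the 5% and the Table 1-2 counts may come from different sets of studies.

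**Precision of the rows proposed below.** At 5% per arm the half-width is 1.96 × √(2 × 0.05 × 0.95/2,000) = 1.35 points, before any non-serious TB is added. For non-serious infections of interest the documents give no rate; an assumed 1% to 5% per arm gives ±0.62 to ±1.35 points.

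**The case against.** The strongest reply is that this is a documented amendment. RAP 2.2.1 points to the changes, and 2.2.3 states each one with its reason. The RAP was final on 18 October 2018 and unblinding was on 2 January 2019. There are no hypothesis tests, so overlapping rows inflate no error rate. All of that stands, and the point is not one of concealment or data-driven choice.

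It is also fair that non-serious TB is not lost from interval estimation. RAP 2.2.3 says its infections-of-interest definition covers everything in Appendix 2, which lists TB, so these events fall in a row with a difference and CI. They cannot be identified there, and they are not where the protocol also put them.

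Some overlap is the protocol's own: TB is in the first endpoint by name and in the second through Appendix 2. This stands for TB. For other serious infections it depends on what the word non-serious qualifies, and the RAP itself reads the whole endpoint as non-serious.

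Finally, a RAP Addendum of 13 December 2018 adds safety analyses, and the table shells are in a separate document. Neither was supplied, so the missing estimates may be planned there.

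**Conclusion.** The point holds in a limited form. In the supplied text, neither infection endpoint as the protocol words it receives the promised difference and 95% CI. Three things are missing or blurred: TB cannot be seen together with the serious infections; non-serious infections of interest regardless of causality are not estimated at subject level; and serious infections of interest (about 1.3% to 1.5% of subjects in earlier trials) count in both rows.

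A reader might infer more than this.

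- *That two AESIs go unestimated.* The serious-infections row is the protocol endpoint less one component, non-serious TB, and every serious infection in the SOC still contributes to an interval.
- *That a TB effect of a particular size would be missed.* The documents give no rate for non-serious TB, so no such size can be supported.
- *That adding serious events costs precision in the second row.* A wider absolute interval there only reflects a higher event rate.

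The overlap figure assumes that the Table 1-2 category matches the serious part of the RAP's infections-of-interest row, and that this trial's rates resemble those of the earlier trials. No sample size or error rate depends on the point.

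**What to change.** Keep the RAP rows. Add two supplementary rows to 9.5.12 and Tables 2.05 and 2.06, with the same difference and 95% CI:

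- (a) serious infections, or any event in the TB query regardless of seriousness;
- (b) non-serious infections of interest per protocol Appendix 2, that is, the existing derivation with AESER ne 'Y', regardless of causality. Keep TB in this row, as Appendix 2 lists it, and footnote its overlap with row (a).

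Also footnote that the RAP's two rows differ from the protocol definitions and that serious infections of interest appear in both. If the Addendum or shells already contain these rows, a cross-reference is enough.

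The flags come from variables already in the AE dataset. The cost is two derivations and two extra table rows. Since the Week 52 analysis was declared complete on 7 February 2019, the rows should be labelled as supplementary; their definitions come from the protocol, so they are not data-driven.
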